
### Auditory steady state response (ASSR) and Gamma band oscillations

Gamma band oscillations (30-80 Hz) are thought to play a critical role sensory and cognitive processing, and in the pathophysiology of a number of neuropsychiatric disorders. The auditory steady state response (ASSR) is a widely used non-invasive electroencephalography (EEG) technique to study cortical gamma oscillations in auditory cortex. The ASSR evoked power is thought to be regulated by interaction of NMDA receptor and parvalbumin (PV) gamma aminobutyric acid (GABA) inhibitory interneuron activity on sensory cortical pyramidal [50, 51]. Ketamine and NMDA antagonists dose-dependently increases ASSR power and gamma oscillations [52, 53] and causes increased cortical excitability likely by shifting excitatory/inhibitory balance at the circuit level [25, 54, 55]. Further, there has been recent initial validations of ASSR at 40 Hz frequency as a potential marker of NMDA activity [56]. Only one study looking at ASSR using MEG study reported no change in MDD patients compared to healthy subjects but significantly larger ASSR power if compared with BD patients [57]

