Exploratory Aim: To investigate Ketamine's acute excitatory glutamatergic effect on cortex as indexed by the ASSR. The first goal of the study is to deploy auditory steady state response (ASSR) and gamma band oscillations as a marker of Ketamine's early excitatory effect on cortex. We previously studied the feasibility of quantifying the effect of pharmacological manipulations on cortical ASSR power. We studied the effect of amphetamine, which increases synaptic dopamine neurotransmission. Twelve healthy subjects (mean age  $30.3 \pm 10$ , M:F 7:5) took part in a double-blind, cross-over, placebo-controlled study of single-dose amphetamine (0.5 mg/kg) administration. Subjects performed the ASSR task, involving auditory click trains consisting of binaural presentations of 1 ms duration tones repetition frequencies of 40 Hz, 30 Hz, or 20 Hz. To ensure attention to stimuli, click trains were presented as an oddball paradigm. Electroencephalographic (EEG) data during task performance were collected on a 128 channel Geodesic Sensor Net. Off-line de-noising and averaging will be performed with EEGLAB (62), and wavelet analyses with Brain Vision Analyzer. The average evoked gamma power was derived for the 40 Hz stimuli over the interval 225–525 ms after stimulus onset. Amphetamine showed decreases in gamma power specifically to the 40 Hz stimuli ( $t=2.3$ ,  $p<.05$ ,  $d_z=0.66$ ). Time frequency plots of gamma power after amphetamine for 40 Hz stimuli demonstrated amphetamine induced decreased gamma power. ASSR-EEG paradigm may be well-suited to tracking Ketamine induced modulations in gamma oscillations as implemented in this project

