external control of the MagPro system. EMG readings may be obtained from the APB muscle. TMS stimulation will be applied to the corresponding region of the contralateral primary motor cortex. The optimal coil position will be determined by moving the coil in 1-cm increments over the motor cortical area while delivering magnetic pulses and by observing maximal contraction of the contralateral APB. The procedure may be repeated for the opposite hemisphere. The main purpose of this study is to examine the cortical excitability measures after Ketamine. Resting motor threshold (RMT) is defined as the stimulation intensity eliciting an MEP greater than 0.5 mV in 5 of 10 trials with a relaxed APB. Intra-cortical facilitation (ICF) is defined as subthreshold conditioning stimulus set at 80% of resting MT calibrated to produce an average MEP of 0.5- to 1.5-mV peak-to-peak amplitude in the contralateral APB. A suprathreshold test stimulus follows conditioning stimulus between 10-20 milliseconds (ms) (55). Conditioning stimuli may be delivered to left Dorsolateral Prefrontal Cortex (DLPFC) or Brodmann Area 6 or Motor cortex prior to the test stimulus in 1 of 3 random inter-stimulus intervals 10 ms (ICF-10), 15 ms (ICF-15), and 20 ms (ICF-20) for ICF measures. The sequence of administration will be counterbalanced to reduce order effects. For ICF, the change in test stimulus MEP amplitude of each inter-stimulus interval was expressed as a percentage of the mean unconditioned MEP amplitude (55). TMS will be applied concurrently with EEG recordings. **EEG/EMG Acquisition and Analysis** - EEG sessions will be conducted in a sound-attenuated room lit with a low-level ambient light. EEG Brain Products Brain Amp MRPlus 64 channel system is used to acquire EEG data. EEG signals are recorded with a 64 channel cap at a high sampling rate (500 Hz) from the entire scalp, with signals amplified by a shielded, MR-compatible amplifier. The software, Brain Vision Recorder, will be used to coordinate EEG recordings with EPrime. Continuous data will be filtered off-line with a .2- to 100-Hz bandpass filter with a 60-Hz ideal notch filter. ASSR Epochs are defined as -500 to 1000 ms relative to stimulus onset adjusted to a -350 to -150-ms prestimulus baseline. Ocular and ECG artifacts will be removed with ICA-based detection and correction methods (EEGLab); [59]. Data will be re-referenced to average reference. EMG data will be obtained using the Brain Amp ExG amplifier which allows for up to 8 simultaneous bipolar recordings at a 5-kHz sampling rate via the same software as EEG data. MEP epochs will be defined as -200 to 300 relative to stimulation. ICF trials will be time adjusted to align the second pulse with single pulse trials, and MEP amplitudes will be determined as the peak to be difference identified between 10 and 50 ms post-TMS pulse. Software and hardware for the analysis of EEG/EMG data, include state-of-the-art analytic and statistical packages (e.g. EEGLab, Brainstorm, Matlab, and SPSS).

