
**OPTIONAL: ASSR/EEG paradigm:** Task - Patients will wear ER-3A insert earphones (Etymotic Research, Elks Grove, IL, USA) for auditory stimuli and will be seated ~80 cm from an LCD computer monitor used to present visual stimuli. All stimuli are presented using E-Prime software (Psychological Software Tools, Pittsburgh, PA, USA). Click trains of 500-ms duration will be presented binaurally at  $65 \pm 5$  dB. The click train repetition frequencies will be 40 Hz and presented in the context of an auditory oddball paradigm to ensure participant attention to the stimuli. Standard stimuli will be click trains with individual clicks being 1-kHz carrier frequency whereas Oddball stimuli will be click trains with clicks of 2-kHz carrier frequency. During click train presentation and for 200 ms after click train cessation, the screen remained blank (black). Participants will be then prompted by the appearance of a central fixation cross to respond by button press with either their left index finger for Standard stimuli (110 trials per block) or their right index finger for Oddball stimuli (10 trials per block). Behavioral analyses will be conducted to confirm attention to task but only correct Standard trials will be submitted for EEG analyses.

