### Summary

We will pre-screen potential participants over the phone to minimize the invitation to non-eligible participants. During the screening visit, we will screen patients for eligibility. Patients will then arrive for their study Day # 2(Baseline), when they will get blood draws (optional), complete questionnaires and undergo TMS-EEG. Patients will come to our inpatient psychiatric hospital facility on the another day (Day # 3) , where they will be given ketamine by the study nurse. During the infusion, patients will be asked constantly about "how they feel" and will be monitored continuously from psychiatric nurse and the attending Anesthesiologist. EKG and pulse-oximetry will be monitored throughout the procedure to check for hemodynamic changes. After the completion of 40 min infusion, patients will rest for two – four hours under the observation of clinical nurse and, reassessed again by psychiatrists at 2 hours after infusion. Patients may be undergoing EEG/ASSR at 10minutes, 40 minutes and at 4 hours after infusion and blood tests after infusion(40 minutes) and 2-4 hours after infusion. Patient will then

have undergo TMS-EEG & EMG at 4 hours. Patient will be discharged to a responsible adult who will accompany the patient home. Patients will be invited again for day #4 (24 hours after infusion), where they will have to complete TMS-EEG & EMG, EEG/ASSR(optional) and blood tests(optional). They will be invited again for just TMS 7 days after infusion. Patients may be contacted every day after the infusion by telephone to check on their physical and mood status and will be scheduled for a clinical visit with the psychiatrists on days 1, 4, and 7 for a follow up assessment of mental state.

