3. *Study Medication.* Side effects associated with ketamine injection are rare and, if any, of transient duration. The most commonly reported side effects during a 4 hour period after infusion include feeling strange or unreal (58.3%), abnormal sensations (54.2%), blurred vision (50.0%), feeling drowsy or sleepy (48.5%) and headaches (30-40%). Based on previous evidence, we do not expect ketamine to impair cognitive functions such as memory, attention or language. If patients are currently taking certain medications on a daily basis within 24 hours prior to and / or after receiving ketamine, they will not be able to take these medication(s) while receiving a ketamine infusion without clearance or approval of the physicians involved in administering ketamine. Medications include: Sedatives (e.g., clonazepam, lorazepam, alprazolam); Antibiotics (e.g., azithromycin, clarithromycin); Antifungal agents (e.g., ketoconazole); Tramadol. This is due to concerns for potential increased sedation or trouble breathing. The risk of addiction to ketamine for a single –dose study is very rare.

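### ASSR power is computed from correctly answered trials only, with no matching of trial counts across sessions, so a change in accuracy after ketamine can bias the within-patient comparison

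*Combined protocol and SAP*

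**What the plan says.** The ASSR/EEG paradigm (Study Design and Procedure) presents 40-Hz click trains of 500 ms in an oddball task. Each block has 110 Standard and 10 Oddball trials; the number of blocks is not given. The patient answers by button press once a fixation cross appears, 200 ms after the clicks end. Behaviour is used to confirm attention, and "only correct Standard trials will be submitted for EEG analyses". No minimum count and no matching of counts between sessions is stated. Ocular and ECG artefacts are corrected by ICA and no epoch-rejection rule is given, so accuracy is the only stated factor that sets how many trials are averaged.

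The measure appears in the Exploratory Aim, for the earlier amphetamine study: "The average evoked gamma power was derived for the 40 Hz stimuli over the interval 225–525 ms after stimulus onset". It is not restated as this trial's endpoint, but the same paragraph presents the paradigm as suited to this project. Under EEG/EMG Acquisition and Analysis, ASSR epochs are "adjusted to a -350 to -150-ms prestimulus baseline", without saying whether this applies to voltage or to power.

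The background gives the expected direction: "Ketamine and NMDA antagonists dose-dependently increases ASSR power and gamma oscillations". On timing, the Summary says "Patients may be undergoing EEG/ASSR at 10minutes, 40 minutes and at 4 hours after infusion", with an optional session at 24 hours. The Statistics section does not mention ASSR.

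**The concern.** Evoked power is the power of the trial average. Averaging shrinks noise but does not remove it, and the remainder is always positive and grows as trials are lost. A rule that lets the patient's behaviour decide the number of trials therefore lets behaviour move the estimate, even if the auditory response is unchanged.

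Ketamine could affect that behaviour. The study-medication risks, for the four hours after infusion, list drowsiness at 48.5% and feeling strange or unreal at 58.3%. A missed or wrong-hand press removes a trial whatever the auditory cortex did. Pairing within patient does not help, because the count would change within the patient, and the open-label design has no control session to show the artefact. What is at stake is whether a change in ASSR after infusion can be read as a cortical effect rather than as a change in the number of trials averaged.

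**Working it through.** **Inputs from the protocol.** 110 Standard trials per block; correct trials only; 20 enrolled with 20% attrition, so 20 × 0.8 = 16 completers; two-sided 5% level.

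**Assumed, because the protocol gives no figure.** One block (three as a variant); 95% correct before infusion; 90%, 80%, 70% or 50% after; single-trial signal-to-noise power ratio (SNR) at 40 Hz from 0.01 to 0.5; SD of within-patient relative change 30% or 50%.

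**The plan's own figures.** None exists for this bias. The earlier ASSR effect reproduces: 2.3/√12 = 0.664, against 0.66 stated. The Power Analysis, which rests partly on ASSR data, states 95% for d = 0.9 and n = 15. A normal approximation gives Φ(0.9√15 − 1.96) = 93.65%, an exact two-sided paired t test 89.95%, and a one-sided one 95.2%. Nothing below depends on this.

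**Step 1: expected evoked power.** Let S be true evoked power, s² single-trial noise power and N the trials averaged. The average has noise power s²/N, so

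E[P] = S + s²/N.

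**Step 2: inflation with no true change.** With SNR = S/s²,

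inflation = (SNR + 1/N₁)/(SNR + 1/N₀) − 1.

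For one block, N₀ = 0.95 × 110 = 104.5. At 80% correct, N₁ = 88; at SNR 0.05 this gives (0.05 + 0.01136)/(0.05 + 0.00957) − 1 = 3.0%. At 50% correct, N₁ = 55 and (0.05 + 0.01818)/(0.05 + 0.00957) − 1 = 14.5%.

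| Correct after infusion | SNR 0.01 | 0.05 | 0.1 | 0.5 |
|---|---|---|---|---|
| 90%, one block | 2.7% | 0.9% | 0.5% | 0.1% |
| 80%, one block | 9.2% | 3.0% | 1.6% | 0.4% |
| 70%, one block | 17.5% | 5.7% | 3.1% | 0.7% |
| 50%, one block | 44.0% | 14.5% | 7.9% | 1.7% |
| 70%, three blocks | 8.6% | 2.1% | 1.1% | 0.2% |
| 50%, three blocks | 21.8% | 5.4% | 2.8% | 0.6% |

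**Step 3: the baseline.** Take a fall from 104 to 55 trials at SNR 0.05, with s² = 1.

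- Voltage baseline only: the formula gives (0.05 + 1/55)/(0.05 + 1/104) − 1 = 14.4%; simulation (3,000 repetitions) gave 13.6%. The bias is upward.
- Subtractive power baseline: prestimulus power has expectation s²/N, so the difference is S for any N. Simulation gave −0.2%. The bias cancels.
- Ratio or decibel power baseline: the ratio of expectations is 1 + N × SNR, which falls from 6.2 to 3.75, or 10 log₁₀(3.75/6.2) = −2.2 dB. Simulation, averaging decibel values over sessions, gave −2.6 dB. The bias reverses.

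**Step 4: effect on a paired test.** With 16 completers the noncentrality is (bias/SD) × √16. For a 10% bias and SD 30% it is 0.333 × 4 = 1.33.

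| Bias | Rejection rate, SD 30% | SD 50% |
|---|---|---|
| 2% | 5.7% | 5.3% |
| 5% | 9.6% | 6.6% |
| 10% | 23.9% | 11.6% |
| 20% | 70.3% | 32.2% |

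**Step 5: matched counts.** If every session of a patient uses the same N, s²/N is the same in each, and the artefactual difference is zero for any SNR, number of blocks or baseline method, provided s² itself does not change.

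**The case against.** The strongest reply is that the trigger may not occur. The protocol contains no accuracy data, and the risk section that lists drowsiness also says that memory, attention and language should not be impaired. The task is easy to pass on Standards: they are 110 of 120 trials, so a patient who always pressed left would score 100% on them. Large losses would need many omitted or reversed presses. Blurred vision is weak support, because the discrimination is auditory and the cross is only a prompt. This stands: the fall in accuracy is a risk to guard against, not an expected result.

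Second, restricting to correct trials serves the protocol's aim of ensuring attention. Analysing every trial regardless of response would admit inattentive trials, possibly more of them after drug. This stands too, and it is why the all-trials analysis belongs in a sensitivity check. In its favour, the prompt comes at least 500 + 200 = 700 ms after onset, later than the 225–525 ms window, so a wrong press need not spoil the EEG of that trial.

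Third, ASSR is exploratory and optional. That limits the consequence without removing it, since the Exploratory Aim calls it the study's first goal and ASSR data feed the sample size.

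**Conclusion.** The concern holds in conditional form. As written, the plan lets a behaviour-dependent trial count enter the within-patient ASSR comparison. If accuracy falls after ketamine and the baseline acts on voltage, evoked power is biased upward, in the hypothesised direction. The amount ranges from negligible (0.4% for a fall to 80% correct at SNR 0.5) to material (44.0% for a fall to 50% at SNR 0.01), both for one block. The largest figures need low SNR, few blocks and heavy trial loss together.

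A reader might infer that a rise at 10 and 40 minutes that fades by 4 or 24 hours would be an artefact, or that the plan is bound to produce a false increase. The documents do not support either. The side-effect rates cover the four hours as a whole, with no time course. Accuracy, SNR and block number are not given, and an unspecified baseline method leaves the direction open. The Summary also does not explicitly list an ASSR session before infusion, so even the reference session has to be assumed. The point is worth acting on because the safeguard costs little, not because bias has been shown.

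**What to change.** In the ASSR/EEG paradigm section:

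1. Keep correct Standard trials as the main set. Within each patient, randomly subsample every session to that patient's smallest session count before computing evoked power, and average over repeated subsamples. Set a minimum acceptable count in advance.
2. Report trial counts and accuracy by time point.
3. State the power measure for this trial, whether its baseline acts on voltage or power (and if power, by subtraction or ratio), the number of blocks, and which session is the reference.
4. As a sensitivity analysis, use all artefact-free Standard trials regardless of response, also count-matched.
5. Report single-trial prestimulus 40-Hz power by session. Matching removes the artefact only if single-trial noise is unchanged by ketamine, and the protocol's own background says that ketamine increases gamma oscillations. If noise power changes by Δ, a residual of Δ/N remains in evoked power under a voltage baseline.

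The cost is a few lines of analysis code and a short addition to the protocol. The downside is slightly noisier estimates in sessions that had many correct trials.

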**OPTIONAL: Blood Tests:**

**Gene Expression and Methylation:** The study aims to identify alterations in gene expression and methylation markers induced by the ex vivo treatment of peripheral blood mononuclear cells from symptomatic patients with treatment-resistant depression with ketamine and assess their correlations with clinical response (as measured by the reduction in the Hamilton Depression Rating Scale - HDRS). For that end blood samples will be collected from all subjects immediately before the first administration of ketamine, and peripheral blood mononuclear cells will be isolated with Ficoll-Paque®, according to the manufacturer's instructions. Cell will then be re-suspended in RPMI and plated at  $4 \times 10^5/cm^2$ . After recovery for 6 hours, cells will be treated with ketamine or vehicle. RNA and DNA samples will be isolated from peripheral blood mononuclear cells immediately after treatment (2 hours) and interrogated by RNA-sequencing (Ion Proton, Thermo Fisher) and the Infinium MethylationEPIC kit

(Illumina), respectively, according to the manufacturer's instructions. The reduction in the HDRS scores from baseline to post treatment will then be correlated with the alterations in the markers from both analyses, and the markers that show the strongest correlations with the reduction in HDRS will be selected. Moreover, expression and methylation markers will be compared between responsive and non-responsive patients. This will lead to the identification of a 'treatment response biosignature' incorporating information from gene expression and DNA methylation that can predict the response to ketamine in patients. **BDNF:** Ketamine and metabolites levels will be measured at baseline, 40 mins, 2-4 hours and 24 hours after ketamine infusion and serum BDNF tests will be performed at baseline (before each infusion), 2-4 hours and 24 hours after each infusion. Samples will be stored at Behavioral and Biomedical Sciences Building (BBSB) for analysis. BDNF concentrations were quantitatively determined by enzyme-linked immunosorbent assay (ELISA). A trained personnel will collect up to a **total** of 10 8 cc tubes (about 5.4 tablespoons) of blood from one subject in all the visits combined. A maximum of 4 8 cc tubes of blood (2.5 tablespoons) will be drawn per day from an individual.

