#### Clinical markers of glutamate neurotransmission and synaptic plasticity

Substantial evidence has shown abnormalities in glutamatergic neurotransmission causing impairments in neural plasticity in mood disorders [31]. Magnetic resonance spectroscopy (MRS) has been employed to measure brain glutamate and glutamine. MRS Ketamine studies in healthy subjects have been inconsistent, showing no change or increased glutamate or glutamine. One study in TRD patients found Ketamine pretreatment low Glx/glutamate ratio (as a marker of glutamine) in the prefrontal cortex was associated with greater improvement [32]. Proton MRS measurements of glutamate and glutamine, especially at low field MRI, has poor spatial and chemical resolution. A  $^1\text{H}$ - $^{13}\text{C}$ -MRS at high MRI field show sub-anesthetic Ketamine dose increase glutamate/glutamine cycle in rats [33] but these findings require confirmation in human clinical subjects. **Peripheral BDNF levels:** Antidepressant treatment increases brain BDNF expression. While it is currently not possible to measure brain BDNF in patient, peripheral BDNF levels are decreased in patients with MDD [34] and serum BDNF increases is associated with antidepressant treatment response [35]. Ketamine significantly increased plasma Brain Derived Neurotrophic Factor (BDNF) levels in treatment responders compared to non-responders at 4 hours post-infusion [36, 37] and negatively correlated with the depression scores [38]. These results suggest that plasma BDNF at 4 hours post-infusion could be markers of Ketamine treatment response. However it is not clear if the BDNF increase is related to enhanced glutamate neurotransmission or synaptic potentiation.

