### **Statistics**

Normality assumptions for continuous variables will be examined. Where appropriate, outliers will be winsorised and log, square root or reciprocal transformations applied to achieve normality if appropriate. If normality cannot not been achieved, either untransformed or dichotomized scores were used. Baseline characteristics will be compared between responders and non-responders with the Mann-Whitney U test for continuous variables and the chi-square test for categorical variables. Changes between two time-points for continuous variables were tested with paired t tests, and associations between continuous variables will be quantified with the Spearman correlation coefficient. Random effects models will be performed to quantify changes in clinical score and its component items over time and to compare temporal differences between eventual responders and non-responders. Splines will be used to determine differences in the pattern of response over time among all patients and to identify the time at which there was no additional improvement in depressive symptoms. Additionally, the relationship between response status between baseline and end of study calculating sensitivity, specificity, and positive and negative predictive values will be reported. Time to relapse for patients who met response criteria at end point will be estimated with the Kaplan-Meier method. Analyses will be performed with IBM SPSS Statistics (version 19; SPSS, Chicago, Illinois) and SAS (version 9.2; SAS, Cary, North Carolina).

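### Markers are related to response only through an unadjusted HDRS reduction with no stated time point or metric; add a baseline-adjusted regression and report both

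*Combined protocol and SAP*

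**What the plan says.** The optional blood-test section (Gene Expression and Methylation) takes cells before treatment: "blood samples will be collected from all subjects immediately before the first administration of ketamine". Ex vivo, "cells will be treated with ketamine or vehicle", and the resulting alterations in expression and methylation are the markers. Clinical response for this aim is the reduction in HDRS, and "The reduction in the HDRS scores from baseline to post treatment will then be correlated with the alterations in the markers from both analyses". Selection is by rank: "the markers that show the strongest correlations with the reduction in HDRS will be selected". A second analysis is dichotomous: "expression and methylation markers will be compared between responsive and non-responsive patients".

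The Statistics section adds only that "associations between continuous variables will be quantified with the Spearman correlation coefficient". It names no partial correlation, no covariate, and no model of post-infusion HDRS on marker plus baseline. Its random effects models describe the clinical score over time and compare eventual responders with non-responders; markers are not mentioned there. Baseline characteristics are compared between responders and non-responders, also without adjustment.

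Under Clinical assessment, HDRS is scheduled before the study and at 4 hours, 24 hours and 7 days, subject to change by the investigator. The marker analysis does not say which of the three later times it uses, or whether the reduction is in points or percent.

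**The concern.** A change score contains its own baseline. When the slope of post-infusion HDRS on baseline HDRS is below 1, patients who score higher at baseline tend to show a larger fall. A marker associated with the observed baseline score then correlates with the fall and can rise in the ranking, even if it adds nothing about response once baseline is known. Baseline variation that does not carry through to the post-infusion score is also noise in the fall, and it can hide a marker that is unrelated to baseline.

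The section aims at a signature that predicts response to ketamine, from at most 20 patients in an open-label study with no comparator. The choice of outcome scale therefore affects which markers go forward. Three candidate time points and an unspecified metric also leave room to choose the outcome after the data are seen.

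**Working it through.** **The plan's own figure.** None exists for this analysis. The Power Analysis gives 95% for N = 15 and d = 0.9, sized on ASSR and motor excitability. The two-sided paired normal approximation gives Φ(0.9 × √15 − 1.96) = Φ(1.53), or 93.7%; the t test gives 90.0%. Neither bears on the marker correlation.

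**Inputs.** From the documents: 20 patients and 20% attrition, so 20 × 0.8 = 16. Assumed, because the documents give none: ρ, the baseline–post HDRS correlation; k, the post/baseline SD ratio; r, the marker–baseline correlation; and a partial correlation of 0.6 for a truly informative marker. Simulations used normal data, at least 20,000 trials per setting, and two-sided 5% per marker. The reduction is taken in points.

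**Step 1. Reduction and its own baseline.**
corr(baseline, fall) = (1 − ρk) / √(1 + k² − 2ρk)
- k = 1, ρ = 0.3: 0.7/√1.4 = 0.59
- k = 1, ρ = 0.5: 0.5/√1 = 0.50
- k = 1.5, ρ = 0.3: 0.55/√2.35 = 0.36
- k = 1.5, ρ = 0.5: 0.25/√1.75 = 0.19
- k = 2, ρ = 0.5: 0, because ρk = 1; above that the sign reverses.

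**Step 2. Marker associated only with observed baseline HDRS.** Its correlation with the fall is r times the Step 1 value. With r = 0.5 and k = 1 this is 0.5 × 0.59 = 0.30 (ρ = 0.3) or 0.5 × 0.50 = 0.25 (ρ = 0.5). Rejection rates at n = 16, r = 0.5:

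| k | ρ | Spearman on fall | Partial Spearman |
|---|---|---|---|
| 1 | 0.3 | 18% | 5% |
| 1 | 0.5 | 14% | 5% |
| 1.5 | 0.3 | 9% | 5% |
| 1.5 | 0.5 | 6% | 5% |
| 2 | 0.5 | 5% | 5% |

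**Step 3. Power for a marker unrelated to baseline.** Adjustment changes the residual variance by the ratio k²(1 − ρ²)/(1 + k² − 2ρk). At k = 1 this is 0.91/1.4 = 0.65 (ρ = 0.3) and 0.75/1 = 0.75 (ρ = 0.5). A partial correlation of 0.6 therefore shrinks to 0.6 × √0.65 = 0.48 or 0.6 × √0.75 = 0.52 in the unadjusted analysis. At n = 16, over ρ = 0.3 to 0.5:

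| k | Spearman on fall | Partial Spearman | Regression on marker + baseline |
|---|---|---|---|
| 1 | 44–50% | 60–62% | 70% |
| 1.5 | 57–63% | 61–62% | 70% |

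The comparison of like with like is Spearman against partial Spearman. The further rise to 70% comes from using normal data on their own scale instead of ranks, so it depends on normality.

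**Step 4. Marker tied to true severity, HDRS measured with error.** Let pre = T + e₁ and post = T + e₂ plus a uniform shift, with the marker linked only to T and k = 1. Then cov(marker, pre − post) = 0, so the unadjusted correlation is valid. The partial correlation of marker and post given pre is r(1 − ρ)/√[(1 − r²)(1 − ρ²)], which is not zero. With r = 0.5 it is 0.25/0.75 = 0.33 (ρ = 0.5) or 0.35/√(0.75 × 0.91) = 0.42 (ρ = 0.3). Rejection rates at n = 16:

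| r | ρ | Spearman on fall | Partial Spearman | Regression |
|---|---|---|---|---|
| 0.5 | 0.5 | 5.2% | 22.5% | 23.4% |
| 0.5 | 0.3 | 4.9% | 31.8% | 35.8% |
| 0.3 | 0.5 | 4.9% | 9.9% | 9.7% |

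Steps 2 and 4 point in opposite directions. Which is nearer the truth depends on whether a marker follows the observed score or the underlying severity, and the documents cannot settle that.

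**The case against.** The strongest case against the point is Step 4. A reader might infer that the planned correlation is biased and that adjusting for baseline cures it. The documents do not support that. Regression to the mean arises from rating error and transient fluctuation in the baseline score. A laboratory marker may not share that error, particularly as the marker blood is drawn just before infusion on Day 3, while the Summary places the questionnaires on the earlier baseline day. In that setting the unadjusted analysis holds its error rate and the adjusted one does not. This objection stands, and it is why the unadjusted result should not be demoted.

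Other objections also stand in part:
- A reader might take the background statement that "peripheral BDNF levels are decreased in patients with MDD" as evidence that these markers follow severity. It concerns BDNF in patients with MDD. It does not concern a within-patient ketamine-versus-vehicle difference in expression or methylation, nor HDRS severity within treatment-resistant depression. The link to baseline is an assumption.
- A loss of power is not certain. At k = 1.5 partial Spearman gains about 4 points at ρ = 0.3 and loses about 1 at ρ = 0.5. At k = 2, ρ = 0.5 it loses about 3.
- That the reduction is in points is a reading of the text; the plan does not say.
- The section is optional, selects by rank and states no alpha. Per-marker error and power therefore only indicate how the ranking would behave.
- Picking the strongest correlations from RNA sequencing and a methylation array in at most 20 patients, with no stated multiplicity control or validation, is a larger problem that adjustment leaves untouched.

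None of this defends leaving the time point and metric open, or using baseline HDRS in no marker model.

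**Conclusion.** The point holds in a conditional form. The plan relates markers to response only through an unadjusted association with HDRS reduction, and specifies neither time nor metric. If the slope ρk is well below 1, a marker associated with observed baseline HDRS can be selected without adding information on response (14–18% rejections against about 5% at k = 1, r = 0.5). A marker unrelated to baseline can be missed (44–50% power against 60–62% with partial Spearman or 70% with regression). Both effects shrink as ρk approaches 1. The values of ρ, k, r and the partial correlation are all assumptions.

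The efficiency case for a baseline-adjusted model is the firmer part. The direction of any false-positive problem is not established. A reader might also infer that adjustment is the only safeguard open to a single-arm study. It is not a safeguard of that kind: it cannot separate response to ketamine from natural course or expectancy, and it replaces neither a control arm nor multiplicity control. This is a worthwhile correction to an optional analysis, not a threat to the neurophysiological aims.

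**What to change.** In the Gene Expression and Methylation paragraph and in Statistics:
1. Name one post-infusion HDRS time for the marker analysis, and say whether the reduction is in points or percent.
2. Make the marker analysis a regression of post-infusion HDRS on the marker plus baseline HDRS.
3. Report the unadjusted Spearman correlation with HDRS reduction beside it for every marker carried forward.
4. Treat a marker as a candidate only if the two agree in direction. A marker of greater improvement has a negative coefficient for post-infusion HDRS and a positive correlation with the reduction. This is a screen, not proof: in the setting of Step 4 the unadjusted correlation is centred on zero, so the signs can agree by chance.
5. Apply the same pair of analyses to changes in BDNF, RMT, ICF and ASSR against HDRS or MADRS.

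The cost is plan wording, one degree of freedom per model and a second column in the results table. No new data are needed where the scheduled baseline HDRS is obtained. The text should also say that adjustment addresses neither the missing comparator nor the number of markers screened.
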